1.2. Study Flow Chart

Evaluation	Visit 1	Visit 2	Visit 3 Final Visit follow-up Day 22 ± 2/ETV
	Day 1 Baseline	Day 15 ± 2	
Informed Consent	X		
Inclusion/Exclusion Criteria	X		
Pregnancy test for females	X	X	
Eligibility/Enrolment	X		
Demography	X		
Medical/Surgical history (ocular &systemic)	X		
Review of current medical conditions (ocular & systemic)		X	X
Prior and concomitant medications (ocular & systemic)	X	X	X
External Ocular Examination	X	X	X
VAS ocular tolerability assessment	X**	X**	X
SANDE questionnaire	X	X	X
Best corrected distance visual acuity	X	X	X
Slit lamp examination (SLE)	X	X	X
Central corneal sensitivity by Cochet-Bonnet aesthesiometry	X	X	X
Tear collection for Lubricin dosing	X***	X***	X****
Tear Film Break Up Time (TFBUT)	X	X	X
Corneal fluorescein staining (Oxford score)	X	X	X
Schirmer's test (ST) I without anesthesia	X	X	X
Intraocular pressure (IOP)	X	X	X
Self-administration at home	X*	X*	
First Administration at study site	X	X	
Compound Dispensing	X		
Adverse events	X	X	X

*Self-administration at home during the study period

** pre-dose, 15 minutes post-dose, 30 minutes post-dose

*** pre-dose – in both eyes, 15 minutes post-dose in the right eye, 30 minutes post-dose in the left eye

**** both eyes

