7.1.4 Tolerability and Safety Evaluation

AEs

Adverse events (AEs) will be coded by System Organ Class (SOC) and Preferred Term (PT), using the Medical Dictionary for Regulatory Activities (MedDRA).

AEs will be classified as pre-treatment AEs (PTAEs) and treatment-emergent AEs (TEAEs), according to the period of occurrence, as follows:

- PTAEs: all AEs occurring before the first dose of the ID and not worsening after the first dose of the IMD
- TEAEs: all AEs occurring or worsening after the first dose of the ID

Individual PTAEs and TEAEs will be listed in subject data listings. No summary table will be provided for PTAEs. TEAEs will be summarized by dose and overall. The number and percentage of subjects with any TEAE and the number of TEAEs will be tabulated by SOC and PT, seriousness, relationship to treatment and severity.

A summary of adverse events leading to premature withdrawal will be provided, grouped by body system and preferred term.

Visual analogue scale (VAS)

Local ocular tolerability score will be performed before any ophthalmic assessment at a given study visit. Specific ocular symptoms to be assessed with the VAS include: dryness, foreign body sensation; burning/stinging; itching; pain; sticky feeling; blurred vision; photophobia. Time profile of treatments will be analyzed according to analysis of variance for repeated measure model.

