4.5.1 Not allowed treatments

Use of topical cyclosporine, topical corticosteroids or any other topical medication for the treatment of dry eye in either eye is not allowed during the treatment period.

During the study follow-up period (from day 15±2 to day 22±2), any ocular topical treatments are allowed, including other artificial tears/lubricants as prescribed by the treating physician.

Hormonal contraceptives for females will be allowed.

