8.4.1 Confidence interval precision of the difference in the expected mean VAS changes

Supposing to have a value of -20 mm for all the mean VAS changes (dryness, foreign body sensation, burning/stinging, itching, pain, stick feeling, blurred vision and photophobia) and a standard deviation σ of 10 mm (the 50% of the expected mean VAS change) in the Lubricin 20 µg/mL arm, Lubricin 50 µg/mL arm and Vismed® 0.18% arm, the number of subjects per treatment arm required in order to have a two-sided 95% confidence interval of the difference in means with a precision ω (defined as the length of the confidence interval divided by two) of 9 mm can be calculated according to the following formula (7):

$$N_{\text{per arm}} = \text{ceiling} \left(\frac{2 \sigma^2 z^2_{1-\frac{\alpha}{2}}}{\omega^2} \right)$$

α (2-sided)	ω (precision)	σ	$N_{\text{per arm}}$
0.05	9 mm	10 mm	10

8.4.2 Confidence interval precision of the difference in the expected proportions of subjects reporting at least one TEAE throughout the study

Supposing to have a proportion of subjects reporting at least one TEAE throughout the study of 0.15 (i.e. 15%) in the Lubricin 20 µg/mL arm (π_{T1}) and in the Lubricin 50 µg/mL arm (π_{T2}) and of 0.45 (i.e. 45%) in the Vismed® 0.18% arm (π_C), the number of subjects per treatment arm required in order to have a two-sided 95% confidence interval of the difference in proportions with a precision ω (defined as the length of the confidence interval divided by two) of 0.4 (i.e. 40%) can be calculated according to the following formula (8):

$$N_{per\ arm} = ceiling\left(\frac{z^2_{1-\frac{\alpha}{2}} [\pi_{T_j}(1-\pi_{T_j}) + \pi_C(1-\pi_C)]}{\omega^2}\right)$$

α (2-sided)	ω (precision)	π_{T_1}, π_{T_2}	π_C	$N_{per\ arm}$
0.05	40%	15%	45%	10

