8.11 Efficacy analysis

8.11.1 Primary efficacy analysis

The primary efficacy analysis will be performed on the subjects included into the Full Analysis Set.

Subjects will be analysed according to the treatment they actually received.

8.11.1.1 Tolerability using a Visual Analogue Scale (VAS) for dryness, foreign body sensation, burning/stinging, itching, pain, stick feeling, blurred vision and photophobia

The VAS values of each ocular symptom (i.e. dryness, foreign body sensation, burning/stinging, itching, pain, sticky feeling, blurred vision and photophobia) and their changes from day 1 - pre-dose values and day 15±2 - pre-dose values for the study/primary eye and for the non-study/secondary eye will be listed ([Listing 16.2.6.1](#)) and summarised by treatment and time point using descriptive statistics (mean, SD, CV%, minimum, median and maximum) ([Table 14.2.1.1](#)).

The VAS values of each ocular symptom for the study/primary eye and for the non-study/secondary eye will be analysed using an analysis of variance for repeated measures model. The model will include fixed effect terms for time point, baseline covariate (i.e. the day 1 - pre-dose value) and treatment. Time point will be specified as a repeated measurement. An unstructured covariance structure of the R matrix will be used and covariance parameters will be estimated using the restricted maximum likelihood method ([Table 14.2.2.1](#)).

Only the VAS values collected at Visit 1, Visit 2 and Visit 3 will be included into the analysis of variance for repeated measure model.

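### The primary VAS model has no treatment-by-time term and does not name its responses, so it specifies no between-arm difference at Day 15

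*SAP*

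**What the plan says.** SAP 8.11.1.1 analyses each VAS symptom, for each eye, with a repeated-measures model fitted by REML with an unstructured covariance matrix. On fixed effects it says: "The model will include fixed effect terms for time point, baseline covariate (i.e. the day 1 - pre-dose value) and treatment". On the data it says: "Only the VAS values collected at Visit 1, Visit 2 and Visit 3 will be included into the analysis of variance". It names no contrast, confidence interval or comparison visit.

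The footnote to the flow chart (protocol 1.2) puts VAS at Visits 1 and 2 at "pre-dose, 15 minutes post-dose, 30 minutes post-dose". Visit 3 has one reading. That makes seven readings per eye and symptom, all at Visits 1 to 3.

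Four other places bear on the point:

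- Protocol 7.1.4: "Time profile of treatments will be analyzed according to analysis of variance for repeated measure model". The synopsis also asks for group comparisons at each time point.
- SAP 8.4.1 sizes the study on the "two-sided 95% confidence interval of the difference in means with a precision" of 9 mm. The difference is in mean VAS change and no visit is named. It assumes the same mean change in every arm: "Supposing to have a value of -20 mm for all the mean VAS changes".
- SAP 4.5.1, on the follow-up week before Visit 3: "any ocular topical treatments are allowed, including other artificial tears/lubricants as prescribed by the treating physician".
- SAP 8.11.4 gives every secondary efficacy parameter an explicit between-treatment comparison of change at Day 15. The primary VAS endpoint has none.

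**The concern.** A model with treatment and time as main effects only forces parallel arm profiles. Its treatment coefficient is one difference, taken to be the same at every included time, so it cannot show a time profile by treatment. It equals the Day 15 difference only if the arm difference does not change between Day 15 and the other times. That is hard to presume when Visit 3 is off study product with other lubricants permitted.

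The sentence on Visits 1 to 3 excludes no scheduled reading, so three readings are open:

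- **(a)** Day 1 pre-dose is covariate only; Visit 2 pre-dose and Visit 3 are the responses.
- **(b)** As (a), with the 15- and 30-minute post-dose values as responses too.
- **(c)** Day 1 pre-dose is both covariate and response.

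At stake is the primary VAS estimate. The sample size is justified by the precision of a between-arm difference, yet the visible text does not define that difference at the on-treatment visit.

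**Working it through.** **The plan's own figure.** With SD 10 mm and half-width 9 mm, N per arm = ceiling(2 × 10² × 1.96² / 9²) = ceiling(9.49) = 10. This reproduces; the sample size is not in dispute.

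**What the coefficient estimates.** Without an interaction, the treatment effect is a weighted average of the time-specific arm differences, with weights R⁻¹1 / (1′R⁻¹1), where R is the residual covariance matrix. For two responses with SDs s₂ (Day 15) and s₃ (Visit 3) and correlation r, the Day 15 weight is

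w = (s₃² − r s₂s₃) / (s₂² + s₃² − 2r s₂s₃).

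Equal SDs give w = 0.5. At r = 0.5, s₃/s₂ = 0.7 gives 0.14/0.79 = 0.18, and s₃/s₂ = 1.5 gives 1.5/1.75 = 0.86. The weights follow the visit variances, not clinical relevance.

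**Assumptions for the illustration (not document figures unless stated).** True Lubricin minus Vismed difference −9 mm at Day 15; 10 per arm (plan); baseline SD 15 mm; baseline slope 0.5. Keeping the SAP's 10 mm as the SD of change gives residual SD √(10² − 0.5² × 15²) = √43.75 = 6.6 mm. There were 1,500 simulated trials per scenario, with REML, unstructured 2×2 covariance and 26 df intervals.

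**Reading (a), residual SD 6.6 mm:**

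| Visit 3 difference | SD ratio, Visit 3 / Day 15 | Correlation | Mean treatment term | CI contains −9 |
|---|---|---|---|---|
| 0 | 1 | 0.3–0.7 | −4.4 to −4.6 mm | 56–63% |
| −4.5 mm | 1 | 0.3–0.7 | −6.7 to −6.8 mm | 82–86% |
| −9 mm | 1 | 0.3–0.7 | −9.0 mm | 93–94% |
| 0 | 0.7 | 0.5 | −1.6 mm | 11% |
| 0 | 1.5 | 0.5 | −7.7 mm | 90% |

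- Over correlations 0.3–0.7 and ratios 0.7–1.5, with Visit 3 difference 0, the mean runs from −0.1 to −9.4 mm.
- With zero difference at both visits, the mean is 0.0 and coverage of zero is 94%.
- With residual SD 10 mm, equal SDs and Visit 3 difference 0, the mean is −4.5 mm and coverage of −9 is 77–79%.
- A Day 15 contrast averages −8.8 to −9.1 mm with 94–96% coverage in every scenario with a true −9 mm.

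**Reading (b).** There are six responses, with equal SDs, within-visit correlation 0.6–0.9 and between-visit correlation 0.3–0.5. Visit 2 pre-dose has weight 0.12–0.15. If the difference is −9 mm at all three Visit 2 times and 0 elsewhere, the term averages −3.0 to −4.0 mm. If the Visit 2 post-dose differences are −4.5 mm, it averages −2.1 to −2.8 mm. An unstructured matrix has 6 × 7 / 2 = 21 parameters, from 30 subjects.

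**Reading (c).** Slope 1 with treatment effect 0 reproduces the Day 1 pre-dose response exactly, so its residual variance can shrink towards zero and the likelihood rises without limit. With that variance fixed at 100, 1 and 0.01:

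| Visit 1 residual variance | Treatment estimate | Slope | −2 REML log-likelihood |
|---|---|---|---|
| 100 | −3.3 mm | 0.629 | 433 |
| 1 | −0.04 mm | 0.994 | 328 |
| 0.01 | −0.0004 mm | 0.9999 | 209 |

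There is no maximum, and the treatment estimate is driven to zero.

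**The case against.** The three readings are not equally likely. The opening of SAP section 8 lists evaluation time points one per visit, which favours (a). Reading (c) would probably show up as a failed or singular fit, not as a published zero.

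Day 15 is not named for the VAS endpoint. Protocol 7.1.5 lists the variables with Day 15 tests and omits VAS, and SAP 8.4.1 names no visit. An average over post-baseline visits is a defined quantity, if a less useful one.

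SAP 8.3 calls the study exploratory, with no formal test and no regulatory claim. Table 14.2.1.1 gives means and SDs of change by arm and time point, so a reader could compute an unadjusted Day 15 interval. The appendices are redacted, and a table shell might name the responses.

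The size depends on the assumed −9 mm. Under equal SDs and no Visit 3 difference, an approximate check gives 85–88% coverage for a true −4.5 mm and 91–92% for −3 mm. The 11% figure needs Visit 3 to be less variable than Day 15.

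All of this stands, and it limits the consequence. It does not remove the gap. Even on reading (a), the only modelled difference pools an on-treatment with an off-treatment visit and cannot deliver what protocol 7.1.4 and the synopsis ask for. SAP 8.1 has a rounding rule for confidence limits, but limits from this model would describe the common effect, not Day 15.

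**Conclusion.** The concern holds and should be fixed. As written, the primary VAS model yields one common treatment effect from an unnamed set of responses, and the visible SAP specifies no Day 15 between-arm VAS difference or interval. That rests on the text alone. The size rests on assumptions: under reading (a) with equal visit SDs, a −9 mm Day 15 difference that has gone by Visit 3 is roughly halved, and unequal visit SDs move the result widely either way. If the true difference is the same at all included times under (a) or (b), including zero, there is no bias. Because the study is exploratory and Day 15 summaries are planned, the defect limits the primary estimate; it conceals no data and does not affect N.

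**What to change.** In SAP 8.11.1.1:

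1. State that Day 1 pre-dose is covariate only and that Visit 2 pre-dose and Visit 3 are the responses. State the role of the 15- and 30-minute values. The simpler choice is to keep them as acute tolerability in the by-time-point summary (Table 14.2.1.1). Modelling them as separate time points needs 21 covariance parameters, against 3 for two visits.
2. Add treatment-by-visit and baseline-by-visit terms. The first is essential. The second is advisable, but an unbiased Day 15 contrast does not require it under randomisation.
3. Report each Lubricin minus Vismed difference at Day 15 with its 95% CI, and report Visit 3 separately as follow-up.

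The cost is SAP wording before database lock and no new data. With two responses there are 2 + 1 = 3 extra fixed-effect parameters; with six there would be 10 + 5 = 15. The interval is wider than for the pooled term:

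- Residual SD 6.6 mm: half-width about 6.1 mm, against 4.8–5.6 mm pooled.
- Residual SD 10 mm: about 9.3 mm, against 7.3–8.4 mm.
- Equal baseline and Day 15 SDs, SD of change 10 mm, baseline correlation 0.3–0.7: about 7.6–8.6 mm.

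The target in SAP 8.4.1 is 9 mm, so the Day 15 contrast meets it or comes close.

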5.3. Risks and Anticipated Adverse Device Events

Up to now, there are no known anticipated adverse events associated with the use of LUBRICIN EYE DROPS, anyway the occurrence of side effects cannot be excluded.

It must be considered that topical treatment with LUBRICIN EYE DROPS could cause local irritation or allergic reactions. There are no known contraindications to the use of LUBRICIN EYE DROPS.

All examinations and assessments that will be carried out during this study are non-invasive, are commonly used in the management of subjects with dry eye and pose no risk to the subjects. Subjects might feel a slight discomfort during the execution of Schirmer test and a local allergic reaction or irritation from the use of fluorescein may be observed. There are no known contraindications to the use of lubricin or sodium hyaluronate eye drops. No data are available about the embryo and fetal toxicity, therefore the experimental treatment will not be allowed to pregnant women or nursing mothers and women of childbearing potential not using appropriate birth control methods.

Local or systemic adverse device effects after the use of Lubricin or hyaluronic acid eye drop solutions are not described. However, it could be possible to observe local irritation and/or local hypersensitivity reaction to a component of the device.

Besides, immediately after ocular instillation a transient blurred vision could be experienced.

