7 INVESTIGATION EVALUATION PARAMETERS

7.1 Efficacy parameters

7.1.1 Primary efficacy parameters

- Visual analogue scale (VAS) for dryness, foreign body sensation, burning/stinging, itching, pain, stick feeling, blurred vision and photophobia.

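### The primary VAS model gives no between-arm estimate of the acute reaction to the drop at Day 15

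*SAP*

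**What the plan says.** The VAS for eight ocular symptoms is a primary endpoint under the tolerability objective (SAP 2 and 2.1). SAP 7.1.1 then lists it as the primary efficacy parameter: "Visual analogue scale (VAS) for dryness, foreign body sensation, burning/stinging, itching, pain, stick feeling, blurred vision and photophobia". At Visits 1 and 2 it is read three times, "pre-dose, 15 minutes post-dose, 30 minutes post-dose" (Protocol 1.2); at Visit 3 it is read once.

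In SAP 8.11.1.1 the VAS values of each symptom, for each eye, "will be analysed using an analysis of variance for repeated measures model". On its terms: "The model will include fixed effect terms for time point, baseline covariate (i.e. the day 1 - pre-dose value) and treatment". Time point is the repeated factor, with unstructured covariance and REML. On the data: "Only the VAS values collected at Visit 1, Visit 2 and Visit 3 will be included" in that model. SAP 8.11.2 plans no sensitivity analysis.

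The same section lists the VAS values and "their changes from day 1 - pre-dose values and day 15±2 - pre-dose values for the study/primary eye" (and for the other eye), and summarises them by treatment and time point with mean, SD, CV%, minimum, median and maximum (Table 14.2.1.1). The text names no arm difference or confidence interval for these changes.

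**The concern.** The tolerability problems the protocol anticipates are acute. Besides local irritation, it says that "immediately after ocular instillation a transient blurred vision could be experienced" (Protocol 5.3). The 15 and 30 minute readings can show such a reaction, as the rise from the pre-dose reading of the same visit. After two weeks of dosing, that rise compared with Vismed is a central part of the tolerability question.

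The model does not supply it. The sentence that limits the data to the three visits excludes nothing if taken literally, because every VAS reading is taken at one of those visits. It may instead mean one pre-dose reading per visit. Under the literal reading, acute reaction and symptom change are averaged into one number. Under the other, the post-dose readings are not modelled.

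The arm-by-arm table does not fully replace a between-arm estimate. Fluorescein instillation, the Schirmer test and tonometry under topical anaesthetic all fall between the pre-dose VAS and the dose (Protocol 6.1.3 and 6.1.4.1). A within-arm rise therefore includes any effect of those procedures. A difference between arms removes the part they share.

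**Working it through.** **1. The plan's own figure.** SAP 8.4.1 uses σ = 10 mm, ω = 9 mm and two-sided α = 0.05. N = 2σ²z²/ω² = 2 × 100 × 3.8415 / 81 = 9.49, rounded up to 10 per arm. This reproduces and is not disputed. It also shows that the SAP justifies its size by the confidence interval of a between-arm VAS difference. I use 9 mm below as an illustrative effect.

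**2. What the model can estimate.** Take the Day 1 pre-dose value x as covariate only, and as responses the six later readings: Day 1 +15 and +30, Day 15 pre, +15 and +30, and Day 22. The model mean is μ(time) + βx + τ(arm). The arm difference is the same τ at every time point, so the arm contrast of Day 15 post-dose minus Day 15 pre-dose is τ − τ = 0 by construction.

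**3. Size if all readings enter.** Let s be an acute reaction on Lubricin only and d its extra symptom change from Day 15 on. The true arm differences at the six readings are (s, s, d, d+s, d+s, d), and the fitted τ is a weighted average of them.

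- *Equal correlations:* weights are 1/6 each. With s = 9, d = 0: (4 × 9)/6 = 6.0 mm. With s = 9, d = −9: (9 + 9 − 9 + 0 + 0 − 9)/6 = 0 mm.
- *Residual correlation 0.8 within and 0.4 between visits:* weights 0.172, 0.172, 0.123, 0.123, 0.123, 0.287. With d = 0: 9 × (0.344 + 0.246) = 5.3 mm. With d = −9: 9 × (0.344 − 0.123 − 0.287) = −0.6 mm.
- *Same correlations for the raw readings, including Day 1 pre-dose:* the fitted common slope is about 0.68. Residual SD is 10√(1 + 0.68² − 2 × 0.68 × 0.8) = 6.1 mm for the Day 1 post-dose readings and 10√(1 + 0.68² − 2 × 0.68 × 0.4) = 9.6 mm for the others, so the Day 1 post-dose readings dominate. Simulation (400 trials, 10 per arm) gave 7.0 mm with d = 0 and 4.8 mm with d = −9.

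| Assumed truth | Day 15 post minus same-visit pre | Day 15 post-dose difference, Day 1-adjusted | SAP single effect |
|---|---|---|---|
| s = 9, d = 0 | 9 mm | 9 mm | about 5 to 7 mm |
| s = 9, d = −9 | 9 mm | 0 mm | about 0 to 5 mm |

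**4. Size if only pre-dose readings enter.** The remaining responses are Day 15 pre-dose and Day 22, with differences (d, d). The acute reaction s does not appear.

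**5. With treatment-by-time added.** The adjusted arm difference at time t is [Ȳ(Lubricin, t) − Ȳ(Vismed, t)] − β[x̄(Lubricin) − x̄(Vismed)]. Subtracting the Day 15 pre-dose difference from the Day 15 post-dose difference removes the β term. With complete data, what is left is exactly the arm difference in same-visit change. The simulated mean was 8.6 to 9.2 mm in both scenarios, against a true 9 mm.

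**6. Precision of that contrast.** Assume a per-reading SD of 10 mm and pre/post correlation r. The half-width is t(27) × 10√(2(1−r)) × √(2/10), with t(27) = 2.052: 9.2, 7.1, 5.8 and 4.1 mm at r = 0.5, 0.7, 0.8 and 0.9. The Day 1-adjusted difference at a single time point, at correlation 0.5, has half-width 2.056 × 10√0.75 × √0.2 = 8.0 mm. The two are equal at r of about 0.62.

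**The case against.** The strongest reply is that little is lost. SAP 8.3 calls the study exploratory and rules out formal tests against Vismed. Change from Day 15 pre-dose is already tabulated by arm, and treatment-emergent adverse events are the other primary endpoint. The protocol defines tolerability as the VAS itself and asks for its time profile (Protocol 7.1.4), so nothing confines it to post-dose minus pre-dose. All of this is fair. The signal is not missing from the report, and the point should not be graded as if it were. But ruling out tests does not rule out estimates, and SAP 8.4 bases the sample size on between-arm intervals.

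A reader might also draw stronger conclusions that the documents do not support:

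- *That the Day 1 covariate is the cause, so a treatment-by-time term would not help.* The covariate cancels from any within-visit contrast (step 5). What is missing is the interaction and a named contrast.
- *That a 20 mm rise could be hidden between the arms.* The SAP's assumption, "Supposing to have a value of -20 mm for all the mean VAS changes", applies to all three arms, so shared relief cancels against the concurrent control. The 20 mm offset holds only within an arm. A complete offset between arms needs relief that differs by arm, and the documents give no figure for that.
- *That a same-visit reference is always more precise.* It is wider at r = 0.5 (9.2 against 8.0 mm), the two quantities differ, and the documents give no pre/post correlation.

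**Conclusion.** The point holds in this form: under either reading of which VAS values enter, SAP 8.11.1.1 produces no between-arm estimate of the acute reaction at Day 15. If all readings enter, an assumed 9 mm reaction is diluted to about 5 to 7 mm when relief is equal, and to about 0 to 5 mm when Lubricin also relieves 9 mm more. If only pre-dose readings enter, it is not estimated at all. The effect sizes, the per-reading SD and the correlations are assumptions; the ranges illustrate and do not predict. The structural result in step 2 needs none of them. The SAP should be changed, but the exploratory status and the existing descriptive table keep this short of a critical defect.

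**What to change.** In SAP 8.11.1.1:

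- State that the 15 and 30 minute readings at Visits 1 and 2 enter the model as responses.
- Add treatment-by-time point and keep the Day 1 pre-dose covariate.
- Pre-specify, at Day 15, the contrast of post-dose (15 and 30 minutes) minus same-visit pre-dose, for each Lubricin arm minus Vismed, with 95% CI.
- At Visit 1, report the Day 1-adjusted post-dose differences; there the covariate already is the same-visit pre-dose value.
- Report the Day 15 pre-dose difference, adjusted for Day 1, separately as the symptom change. It can stay within the tolerability endpoint.

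A model of the Day 15 same-visit change score is an equivalent option. Day 15 pre-dose should not be used as a covariate, because it is measured after randomisation and may itself be affected by treatment.

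The cost is a few more estimates per symptom and eye, to be read as exploratory and without multiplicity adjustment. The readings are already scheduled and the Day 15 changes already derived, so there is no added visit, procedure or patient burden.

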- Patient discharge

Criteria for Evaluation:

Evaluation of the clinical tolerability, safety and efficacy of treatment with Lubricin eye drops in patients with moderate to severe dry eye, on the basis of the following assessments.

Primary outcomes:

- Tolerability using a Visual analogue scale (VAS) for dryness, foreign body sensation, burning/stinging, itching, pain, stick feeling, blurred vision and photophobia
- Treatment-emergent adverse events (TEAEs), assessed throughout the study

Secondary outcomes

- Ocular surface vital staining with Fluorescein (Oxford scale)
- Schirmer-I test (without anaesthesia);
- Permanence of Lubricin on the Ocular Surface Tear film break-up time (TFBUT);
- Best corrected distance visual acuity (BCVA);
- SANDE questionnaire scores – discomfort improvement entity;
- SANDE questionnaire scores – discomfort improvement speed;
- Signs evaluated by Slit lamp examination (SLE) (blepharitis, eyelid hyoeremia/oedema, lashes, conjunctiva hyperemia)
- Intraocular pressure (IOP)
- Corneal sensitivity by Cochet-Bonnet aesthesiometry

Variables will be compared between groups at each time point.

Statistical Methods:

The data documented in this study will be listed by patient, dose, eye (left and right, if applicable) and evaluation time point.

Appropriate descriptive statistics will be used according to the nature of the variable.

Not available data will be evaluated as “missing values”. The statistical analysis will be performed using SAS® version 9.3 (TS1M1) for Windows® or higher.

A statistical analysis plan (SAP) will be issued before database lock. Final statistical analysis models will be presented in detail in the SAP.

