Visit 3/ETV Final Follow-Up Visit	Days 22±2	
The final visit is defined as the visit performed 7 ± 2 days after last administration (day 21 ± 2). In case of study discontinuation subjects will undergo an early termination visit.
 
The following procedures will be performed:
 
 ➤ Review of current medical conditions (ocular and systemic: including External Ocular Examination) ➤ AE and concomitant medications ➤ Ocular examination in both eyes, consisting of the assessments detailed for the baseline visit (points 1-10), in the same order and with the same intervals ➤ Patient discharge

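### The VAS model in SAP 8.11.1.1 has no treatment-by-time term, so it gives one time-constant arm difference that mixes on-treatment values with off-treatment Visit 3, and its text allows Day 1 pre-dose as both response and covariate

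*SAP*

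**What the plan says.** VAS tolerability is the first of two primary endpoints (Protocol 6.1.2; SAP 2.1). SAP 8.11.1.1 analyses each symptom, for the study eye and for the other eye, with a repeated-measures model (unstructured covariance, REML, Table 14.2.2.1). On the fixed effects: "The model will include fixed effect terms for time point, baseline covariate (i.e. the day 1 - pre-dose value) and treatment". On the data: "Only the VAS values collected at Visit 1, Visit 2 and Visit 3 will be included". No interaction and no contrast is specified, and SAP 8.11.2 plans no sensitivity analysis.

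The protocol describes the purpose differently. Section 7.1.4: "Time profile of treatments will be analyzed according to analysis of variance for repeated measure model". Synopsis: "Variables will be compared between groups at each time point". SAP 1.1, which lists changes from the clinical investigation plan, mentions none here.

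At Visits 1 and 2 the VAS is taken three times (Protocol 1.2): "pre-dose, 15 minutes post-dose, 30 minutes post-dose". Visit 3 has one reading. On its timing, Protocol 6.1.3 says: "The final visit is defined as the visit performed 7 ± 2 days after last administration". In that interval, under SAP 4.5.1, "any ocular topical treatments are allowed, including other artificial tears/lubricants as prescribed by the treating physician".

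The same section of the SAP also summarises VAS values and changes from Day 1 pre-dose by arm and time point (Table 14.2.1.1). SAP 8.3 calls the investigation exploratory, with no formal comparison of Lubricin with Vismed.

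**The concern.** There are two linked problems.

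**One coefficient for all visits.** A treatment main effect without an interaction assumes parallel arm profiles. The model therefore cannot display a time profile or give a separate modelled difference at any visit. What it estimates is a covariance-weighted average of on-treatment differences and the difference a week after stopping, when patients may be using other lubricants. That average is not the tolerability difference under treatment unless the difference is the same at every included reading.

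**Unclear responses.** The visits are named but the readings within Visits 1 and 2 are not. Visit 1 is listed among the included data while its pre-dose value is the covariate. If that value is also a response, the model tries to explain a variable by itself.

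At stake is the only modelled table for this primary endpoint. SAP 8.4.1 justifies 10 per arm by a "two-sided 95% confidence interval of the difference in means with a precision" of 9 mm for VAS change, yet no listed VAS output clearly delivers that interval at Day 15.

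**Working it through.** **1. The plan's own figure.** Inputs from SAP 8.4.1: SD 10 mm, half-width 9 mm, two-sided 95%.

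N = 2 × 10² × 1.96² / 9² = 9.49, rounded up to 10 per arm. This reproduces. The half-width achieved at 10 per arm is 1.96 × 10 × √(2/10) = 8.77 mm.

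**2. What the treatment coefficient estimates.** The planned mean is μ(time) + β × baseline + τ(arm), and τ has no time index. With arm differences δ at the included readings and residual covariance R, the estimate targets Σ w·δ, where w = R⁻¹1 / (1′R⁻¹1). If the responses are Visit 2 pre-dose and Visit 3, with residual SDs s2 and s3 and residual correlation r:

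w3 = (s2² − r·s2·s3) / (s2² + s3² − 2r·s2·s3)

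Take s2 = 10 mm and a true difference of 10 mm at Day 15 and 0 at Visit 3. The 10 mm difference, s3 and r are assumptions. The SAP's 10 mm is the SD of change, used here as a residual SD for illustration.

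| s3 (mm) | r | w3 | Estimate (mm) |
|---|---|---|---|
| 10 | 0.3, 0.5 or 0.7 | 0.50 | 5.0 |
| 8 | 0.3 | 76/116 = 0.655 | 3.45 |
| 8 | 0.7 | 44/52 = 0.846 | 1.54 |
| 12.5 | 0.3 | 0.345 | 6.55 |
| 12.5 | 0.7 | 12.5/81.25 = 0.154 | 8.46 |

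A difference of 10 mm at both visits gives 10 mm in every row. Differences of +10 and −10 mm give 0 at equal SDs.

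**3. Simulation of the same case.** Three arms of 10, SD 10 mm per reading, all raw correlations 0.5 (so the SD of change is 10 × √(2 × 0.5) = 10 mm, matching the SAP), 1,500 trials, REML. Monte Carlo error is 0.05 to 0.15 mm.

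| True 9 mm difference at | Planned model | Day 15 contrast with interaction |
|---|---|---|
| Day 15 only | 4.33 | 8.85 |
| Visit 3 only | 4.45 | −0.04 |
| Both | 8.95 | 8.90 |

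**4. Day 1 pre-dose as response and covariate.** The introduction to SAP section 8 lists three evaluation time points, one per visit. Combined with the sentence naming Visits 1 to 3, this allows pre-dose Visit 1, pre-dose Visit 2 and Visit 3 as the responses. The Visit 1 response then equals the covariate. A slope of 1, an intercept of 0 and τ = 0 fit Visit 1 exactly, its residual variance goes to 0, and the likelihood keeps rising as it does so. A non-zero τ would spoil the perfect fit, so τ is driven to 0.

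In one simulated data set of 30 subjects, both Lubricin arms were 10 mm lower than control at Visit 2 and equal at Visit 3 (iterated generalised least squares):

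| Iteration | Slope | Treatment estimates (mm) | Visit 1 residual variance |
|---|---|---|---|
| 0 | 0.580 | −4.40, −4.22 | 26.1 |
| 5 | 0.877 | −1.22, −1.17 | 2.2 |
| 20 | 0.997 | −0.030, −0.029 | 0.0014 |
| 55 | 1.000 | about −0.000005 each | covariance matrix singular |

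The same data with only Visits 2 and 3 as responses gave −5.96 and −5.71 mm.

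**The case against.** The other side has a fair case, and several parts of it stand.

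- **The SAP is not silent on the data, and the model does give an arm difference.** A reader might infer that no response set is stated, or that the model yields no difference at all. Neither is right. The visits are named, and the model gives one difference, assumed constant over time. What is missing is the reading within Visits 1 and 2, the role of Visit 1 pre-dose, and a time-specific difference.
- **Table 14.2.1.1 covers part of the need.** Mean change from baseline and SD by arm and time point, with the arm sizes, allow an approximate unadjusted interval at Day 15 by hand. Only the baseline-adjusted, model-based interval is absent.
- **All six post-baseline readings as responses.** A reader might infer that readings just after the first drop would dominate the estimate. Section 8 of the SAP defines three visit-level time points, which makes that set unlikely, so the point does not rest on it.
- **The degenerate fit would show itself.** Probably so. How SAS would react is not known from the documents; it may stop or flag the fit. This part is a wording defect, not hidden bias.
- **The planning assumption is no difference.** SAP 8.4.1 assumes −20 mm in every arm. If arms are equal at every reading, pooling causes no bias. The 9 and 10 mm differences above are illustrations, not expected effects.
- **Redacted appendices.** They may name the readings or show the table layout. They would not alter the list of fixed effects in the text.

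**Conclusion.** The point holds. As written, the model gives one averaged arm difference that includes off-treatment Visit 3, and it cannot deliver the time profile or a modelled comparison at each time point. That conclusion follows from the fixed-effects list and needs no assumed figure.

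The size does depend on assumptions. With Visits 2 and 3 as responses and equal SDs, a Day 15-only difference is halved. Over Visit 3 SDs of 8 to 12.5 mm and residual correlations of 0.3 to 0.7, 15% to 85% of it is recovered, and there is no bias if the difference is equal at both visits. It would be wrong to infer that the model always understates the on-treatment effect: a difference arising only at Visit 3 would be reported in part as a treatment effect.

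If Day 1 pre-dose is also a response, which the text permits, the treatment estimate goes to zero whatever the data show.

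A reader might also infer a risk of a false efficacy or safety claim. SAP 8.3 rules out formal tests and regulatory claims, so the documents do not support that. The harm is an uninformative or degenerate model table for a primary endpoint. The change should be made, but the trial does not fail without it.

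**What to change.** In SAP 8.11.1.1:

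1. Use post-baseline VAS values only as responses, name each reading, and keep Day 1 pre-dose as covariate only.
2. Add a treatment-by-time-point term.
3. Report each Lubricin arm minus Vismed with a 95% CI at day 15±2 pre-dose.
4. Report Visit 3 separately, labelled off-treatment.

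Items 1 and 2 are both needed. Dropping Visit 3 alone leaves the degenerate case in place. Adding the interaction alone frees the Day 15 contrast there, which becomes the plain difference in change, but the fit stays singular.

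The cost is SAP wording and extra contrasts in Table 14.2.2.1; sample size and visits do not change. Each contrast is less precise than the pooled one: in the simulation the SD of the estimate rose from 3.2–3.6 to 3.8–3.9 mm. The tighter figure, however, belongs to a mixed quantity. With SD 10 mm and 10 per arm, the single-visit half-width is 8.8 mm by z and 9.2 mm by t (26 df), close to the planned 9 mm. With 9 per arm after the 10% drop-out in Protocol 7.3, it is 1.96 × 10 × √(2/9) = 9.2 mm by z, or 9.8 mm by t (23 df).
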